Patient demographic and medical characteristics (e.g., comorbid conditions) will be obtained directly from EpicCare. Socioeconomic status will be assessed by asking patients about their education, occupation, and income. Patient and bed partner relationship quality will be assessed using the 4-item version of the Dyadic Adjustment Scale (DAS-4), one of the most widely used measures of couple satisfaction in research and clinical practice.⁷⁶ The 6-item Zarit Burden Interview for Dementia Caregivers is one of the most widely used measures of caregiver burden.⁷⁷ OSA severity will be assessed using the apnea-hypopnea index, the time spent with oxyhemoglobin saturation < 90%, and the lowest value of oxyhemoglobin saturation each retrieved from the polysomnogram report.⁷⁸ All participants will be given an autotitrating CPAP machine that can be monitored remotely. The device will upload objective adherence data to RedCap each morning following use. **Adherence is the average nightly use of CPAP from baseline to designated follow-up times (30 days, 90 days).**

Instruments to measure OSA knowledge and beliefs, depression, sleepiness, quality of sleep, quality of life, self-efficacy to use CPAP, and degree of bed partner involvement in CPAP adherence will be completed by all study participants at **baseline, 30 days, and 90 days**. These instruments have demonstrated reliability and validity and have been used in previous

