studies of OSA and CPAP adherence. Depression, a potential factor confounding the relationship between the presence of sleep apnea and CPAP adherence, will be assessed using the 9 item Patient Health Questionnaire (PHQ-9).⁷⁹ It performs well among diverse patient populations.⁸⁰ The 8-item Epworth Sleepiness Scale (ESS) measures the propensity to fall asleep in eight unique situations.⁸¹ Scores on the ESS are positively associated with OSA severity,⁸² and they improve with CPAP treatment. The 8-item short version of PROMIS Sleep Disturbance Index will be used to assess self-reported perceptions of sleep quality, sleep depth, and sleep restoration. It has greater measurement precision than the ESS and the Pittsburgh Sleep Quality Index.⁸³ The impact of sleepiness on functional status will be assessed using the 10-item Functional Outcomes of Sleep Questionnaire (FOSQ-10). Quality of life will be assessed with the 12-item Medical Outcome Survey Short Form (SF-12).⁸⁴ Sleep-related quality of life will be assessed using the Calgary Sleep Apnea Quality of Life Index (SAQLI). Self-efficacy, or confidence in one's ability to use CPAP when faced with difficulties, will be assessed using the Self Efficacy Measure in Sleep Apnea (SEMSA).

DATA ELEMENT	SOURCE

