13.0 Recruitment Methods

Prior to enrollment of the first subject, sealed envelopes containing participant computer-randomized study arm assignment will be created. To assure balanced but unpredictable assignments of participants we will use permuted block randomization, stratified by study site.^{88,89} Study flyers will be distributed to sleep providers to distribute to eligible patients who can contact study staff for enrollment. Research assistants will obtain automated digital reports from EpicCare of patients who have received an at-home or in-lab diagnostic sleep study over the previous 48 hours and an order for initiation of CPAP. They will review EpicCare to verify eligibility (see Table above). Study staff will mail a study brochure and consent form to patients. Those who do not respond within 72 hours will receive a phone call to confirm patient and bed partner eligibility and to explain the study in detail. Upon obtaining verbal confirmation, staff will arrange a date and time to meet with patients and their bed partners in person to obtain written consent and to administer baseline study instruments. After completion of these initial tasks, staff will open envelopes to determine subject study arm assignment. Only the sleep technologist, the research assistants who enroll the patients and the participants will be aware of study arm assignments. Participants will receive ClinCard payments within 1 week of completion of study tasks. Participants will receive \$50 for completion of the baseline, 30-day, and 90-day instruments (\$150 total / participant paid by ClinCard). Participants will also be reimbursed for public transportation or parking.

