17.0 Data Management and Confidentiality

Our study database will be stored in RedCap (<https://www.project-redcap.org>),⁹⁰ a secure, open-source software application regularly utilized by [name] research teams. RedCap runs on the MetroHealth server and therefore is HIPAA compliant, provides user-specific data access, and facilitates removal of participant identifying data prior to exporting. It also facilitates double data entry with real-time data validation and data integrity checks. Patient data will be entered directly into the RedCap. Study data will be held for 7 years following study completion. Paper records will be stored in locked filing cabinets within the Center for Reducing Health Disparities (Rammelkamp R209). Mosio will use HIPAA compliant procedures to securely send and receive data between study participants and RedCap.

Because this is a pilot study, a power calculation is not provided.

We will begin our analysis by computing descriptive statistics and using graphical representations to examine all predictor and outcome variables. For each study patient, the primary outcome will be CPAP adherence at 90 days as determined by the mean daily CPAP usage (the total number of hours of CPAP use divided by the number of days observed for the

individual). An intention to treat analytic approach will compare mean daily CPAP usage between intervention and control patients as randomized. Linear mixed effects models using random effects will be used to adjust for clustering of patients within sleep provider. Covariates (fixed effects) will include indicator variables for BMI, AHI, gender, and treatment.⁸⁹ The model assumption that the overall CPAP usage outcome is normally distributed will be tested using the Shapiro-Wilk test. If a significant departure from normality is obtained (and a suitable transformation, such as log, is not found) an alternative approach will be to use a generalized linear (e.g., Poisson regression) model for the overall adherence (CPAP usage rate). A Wald test (with robust estimate of standard error) will be used to test for an intervention effect and a corresponding 95% confidence interval for the intervention effect will be computed. If substantial variability in follow-up times are found (e.g., due to dropout and/or missed visits), a weighting approach (using weights proportional to the number of days observed for each individual in conjunction with the selected model) can be used.

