We will perform primary and secondary analyses like those for Aim 1. However, the outcome variables for Aim 2 analyses will be scales and subscales related to quality of sleep (Epworth Sleepiness Scale, PROMIS Sleep Disturbance Index), functional status (Functional Outcomes of Sleep Questionnaire short version), and quality of life (SF-12, Calgary Sleep Apnea Quality of Life Index) for both patients and their bed partners. If these outcome variables are not normally distributed, we will use proportional odds with random effects by study site and sleep provider to test differences in these ordinal data between arms.⁹¹

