22.0 Consent Process

Each day, research assistants will review electronic health record-generated reports of patients who received a diagnostic sleep study over the previous 48 hours and a prescription for CPAP from their provider. Assistants will review the electronic health record of each patient to confirm eligibility. They will then mail a study brochure and consent form to patients. Those patients that do not respond by 72 hours will be contacted to confirm that both the patient and bed partner are eligible and to explain the study in greater detail. After obtaining verbal confirmation, the staff will schedule a date and time to meet with patients and their bed partners at MetroHealth to fully explain the study, address any questions that patients and partners may have, obtain written consent, and administer baseline study instruments using the IRBs standard operating procedures. Following completion of these tasks, staff will open premade sealed envelopes to determine subject study arm assignment.

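### The stated Aim 2 model leaves out each participant's own pre-randomisation score, a minor loss of precision if baseline and 90-day scores correlate above about 0.3

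*Protocol*

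**What the plan says.** The Aim 2 paragraph of Protocol section 17.0 opens with "We will perform primary and secondary analyses like those for Aim 1". It then names what differs: "However, the outcome variables for Aim 2 analyses will be scales and subscales related to quality of sleep", together with functional status and quality of life, in patients and bed partners, and a proportional-odds model if scores are not normally distributed. That fallback is described only by its random effects.

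The Aim 1 paragraph of the same section describes a linear mixed model with a random effect for sleep provider. On fixed effects it says "Covariates (fixed effects) will include indicator variables for BMI, AHI, gender, and treatment". On inference it says "A Wald test (with robust estimate of standard error) will be used to test for an intervention effect", with a 95% confidence interval.

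Baseline questionnaire data are planned. Section 6.0 schedules at baseline, 30 days and 90 days, for all participants, "Instruments to measure OSA knowledge and beliefs, depression, sleepiness, quality of sleep, quality of life, self-efficacy to use CPAP" and bed partner involvement. Section 13.0 pays for "completion of the baseline, 30-day, and 90-day instruments". Section 22.0 places consent and the baseline instruments before allocation: "Following completion of these tasks, staff will open premade sealed envelopes to determine subject study arm assignment".

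The Aim 2 endpoints in section 4.0 are scores at 90 days. The one objective worded as a comparison with baseline, in section 1.0, concerns CPAP adherence.

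**The concern.** The Aim 1 covariate list was written for CPAP use, which has no pre-treatment value in newly diagnosed patients. Aim 2 carries it over to questionnaire scores, which do have one. The stated model therefore does not use a pre-randomisation measurement of the same quantity that the trial already plans to collect.

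Randomisation keeps the comparison unbiased in expectation with or without the baseline score, so only precision is at stake. With about 10 couples per arm, chance differences between arms at baseline are large. To the extent that baseline predicts the 90-day score, those differences pass into the estimated effect. Against this, each extra covariate costs a degree of freedom, which is not negligible with 20 observations. The question is how strong the correlation must be before adjustment pays.

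**Working it through.** The protocol states that no power calculation is provided, so there is no figure to reproduce.

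**Inputs from the protocol.** 20 patients and 20 bed partners (section 1.0); half of the patients to each arm (section 2.0), so 10 v 10 for either member of the couple; three covariates besides treatment (section 17.0); 7 sleep providers (section 25.0).

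**Assumed.** The correlation r between baseline and 90-day score, varied from 0 to 0.7; one column per covariate; normal scores. Both arms start CPAP after baseline, and section 6.0 says of Epworth scores "and they improve with CPAP treatment", which could lower r.

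**Closed form, provider effect omitted.** Adding the baseline score multiplies residual variance by 1 − r². The small-sample inflation for q random covariates is (N − 3)/(N − 3 − q). With N = 20, going from q = 3 to q = 4 multiplies the variance by (17/13)/(17/14) = 14/13 = 1.077. Residual degrees of freedom fall from 15 to 14, and the t quantile rises from 2.131 to 2.145. Hence

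width ratio = √[(1 − r²) × 14/13] × 2.145/2.131 = 1.044 × √(1 − r²).

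Setting this to 1 gives r² = 1 − 1/1.044² = 0.083, so break-even is r = 0.29.

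**Check by simulation** (10,000 null data sets per r, 10 v 10, three binary covariates, model-based t interval):

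| r | Closed form | Simulated width ratio |
|---|---|---|
| 0 | 1.04 | 1.04 |
| 0.2 | 1.02 | 1.02 |
| 0.3 | 0.996 | 0.99 |
| 0.4 | 0.96 | 0.95 |
| 0.5 | 0.90 | 0.90 |
| 0.6 | 0.84 | 0.83 |
| 0.7 | 0.75 | 0.74 |

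**Sensitivity** (simulated width ratios):

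| Setting | r = 0 | 0.3 | 0.4 | 0.5 | 0.7 |
|---|---|---|---|---|---|
| Random provider intercept, 7 providers, assumed ICC 0.05 | 1.04 | 0.99 | 0.96 | 0.90 | 0.75 |
| Five indicator columns instead of three | 1.05 | 1.00 | 0.96 | 0.91 | 0.75 |
| 8 v 8 analysed | 1.06 | 1.01 | 0.97 | 0.92 | 0.76 |
| Robust HC3 standard error with t | 1.09 | 1.03 | 0.99 | 0.94 | 0.78 |

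With HC2 and a t reference, the ratios match the model-based ones to within 0.01.

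**Chance imbalance.** The baseline difference between arms has SD √(2/10) = 0.45 score SDs. After the three stated covariates this is 0.45 × √(17/14) = 0.49. The share left in the estimate is r × 0.49: 0.15 SD at r = 0.3 and 0.25 SD at r = 0.5. This is the same loss seen in another form, not an addition to the width ratios.

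**Interaction with the robust Wald test.** If that test is applied uncorrected with a 1.96 cut-off, null rejection is already above 5%, and the extra term raises it further:

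| Setting | Without baseline | With baseline |
|---|---|---|
| Three binary covariates, uncorrected | 12–13% | 14–15% |
| Five columns, uncorrected | 16–18% | 18–19% |
| Sandwich clustered on 7 providers, uncorrected | 21–22% | 23–24% |
| HC2 with t reference | about 6% | about 6% |

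The proportional-odds fallback was not simulated.

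**The case against.** The strongest reply is that baseline covariates for secondary questionnaires are ordinary content for a statistical analysis plan, and that plan is not at hand. The covariate sentence does not exclude further terms. Nor can an analysis like that of Aim 1 be a literal copy, because AHI comes from the patient's sleep study and none is described for bed partners, so the Aim 2 covariates need more specification anyway. This stands as a limit on the claim, which concerns the stated model only. But the protocol does more than stay silent: it names a covariate list and carries it over to outcomes for which a better one is available. A plan written to match would inherit the choice.

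A second reply is that any gain rests on an assumed correlation, and that starting CPAP in both arms may lower it. This also stands. At r near 0 the adjusted interval is 4% wider, or 6% with 8 v 8, and with HC3 break-even moves to about 0.4. The downside is nevertheless small beside a 10% narrower interval at r = 0.5 and about 25% at 0.7.

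Third, the extra term slightly worsens an uncorrected robust Wald test. That is true, but the small-sample problem exists without the baseline term and is larger than the increment. It is a reason to pair the two changes, and it adds no weight to this point.

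Finally, a baseline FOSQ-10 is inferred: the timing sentence in section 6.0 does not name functional status. It needs confirming.

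**Conclusion.** The point holds as a minor, optional improvement. The stated Aim 2 model does not use the pre-randomisation score, and at this sample size using it narrows the 95% confidence interval once r exceeds about 0.3. The gain is 4–5% at r = 0.4, 10% at 0.5 and about 25% at 0.7; the loss is 4% at r = 0. The value of r is not in the protocol, so whether this trial would gain cannot be shown from it. These are secondary outcomes of a 20-couple pilot with no power target, the comparison is unbiased in expectation either way, and no conclusion is invalidated. The figures assume normal scores, a linear model and about 10 analysed participants per arm. They change little with a provider intercept, five covariate columns or 8 v 8.

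**What to change.** In the Aim 2 paragraph of section 17.0, state that each linear model includes the participant's own baseline score on the same scale as a continuous covariate, wherever that scale was collected at baseline. Confirm that FOSQ-10 is among those scales. Include the term in the proportional-odds fallback only where that model can be fitted at this sample size.

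For these analyses, also specify a t reference with a small-sample-corrected robust standard error (HC2, for example) or a model-based t interval, in place of an uncorrected robust Wald test.

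The cost is a sentence or two and one degree of freedom per model. No new visits or data are needed, apart from the FOSQ-10 check. If r proves near 0, intervals are about 4% wider, or 6% with 8 v 8. Fixing the choice before outcome data are seen by arm also avoids a later decision to adjust or not.

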1.0 Study Summary

Study Title	A PILOT STUDY TO DETERMINE THE FEASIBILITY OF A COUPLES' ORIENTED INTERVENTION TO PROMOTE CPAP ADHERENCE AMONG AFRICAN AMERICAN PATIENTS WITH OBSTRUCTIVE SLEEP APNEA
Study Design	Randomized Controlled Trial
Primary Objective	Mean CPAP adherence at 90 days
Secondary Objective(s)	Mean CPAP adherence at 30 days Change in mean CPAP adherence at 90 days (compared to baseline) Self-efficacy to use CPAP Patient and bed partner quality of life Patient and bed partner quality of sleep
Research Intervention(s)/ Investigational Agent(s)	Peer motivators Behavioral couple therapy Telemonitoring and feedback
IND/IDE #	N/A
Study Population	African American patients with OSA and bed partner
Sample Size	20 patients and 20 bed partners
Study Duration for individual participants	90 days
Study Specific Abbreviations/ Definitions	OSA Obstructive Sleep Apnea CPAP Continuous Positive Airway Pressure

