We propose to pilot test a couple-oriented intervention in a randomized controlled trial of 20 African American patients diagnosed with moderate to severe OSA and their partners. Half of the patients will receive optimal **usual care currently implemented at MetroHealth**, consisting of sleep therapist-initiated standardized education about OSA, sleep hygiene, and CPAP use; personalized mask fittings; and follow-up at 1 week to troubleshoot problems with CPAP utilization. Participants will follow up with their sleep providers per usual. The remaining patients and their bed partners will receive a **couple-oriented intervention** consisting of guideline-recommended best practices for improving CPAP adherence consisting of sleep therapist-initiated **standardized education for couples** about OSA, sleep hygiene, and CPAP use; personalized mask fittings; and follow-up at 1 week to troubleshoot problems with CPAP utilization. Couples will participate in two couple-oriented support groups led by an African American patient with long standing OSA treated with CPAP and their partner. Patients and partners will receive tailored text messages encouraging adherence. In addition, **couples will receive** five 60-minute **virtual cognitive behavioral couple therapy** sessions with a health psychologist trained in behavioral sleep medicine that will focus on enhancing **couples' knowledge** of CPAP, **patients' self-efficacy** to use CPAP, **couple's relationship dynamics**, and **partners' skill and self-efficacy** in assisting the patient with CPAP adherence.

Primary Aim 1: To determine the impact of a couple-oriented intervention on CPAP adherence.

Hypothesis: Compared to usual care patients, patients who receive the couple-oriented intervention will use CPAP for more hours per night over 90 days (primary outcome).

Primary Aim 2: To determine the impact of a couples-oriented intervention on quality of sleep, functional status, and quality of life of OSA patients and their partners.

Hypothesis: Compared to usual care couples, couples who receive the couple-oriented intervention will have a higher quality of sleep, functional status, and quality of life at 90 days (secondary outcomes).

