4.0 Study Endpoints

Primary Endpoint: Mean CPAP adherence over 90 days

Secondary Endpoints: Mean CPAP adherence over 30 days
Patient and Bedpartner quality of sleep at 90 days
Patient and Bedpartner functional status at 90 days
Patient and Bedpartner quality of life at 90 days

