6.0 Procedures Involved

This is a pilot randomized controlled trial involving 20 African American patients with OSA and their bed partners. Patients will be identified within 48 hours of a new diagnosis of moderate to severe OSA and planned prescription of CPAP by their providers. Patients will be randomized to a usual care arm or a couple-oriented intervention arm and complete the tasks below. All patients will receive auto-titrating CPAP machines equipped with cellular modems upon enrollment into the study. Every morning the machines will use cellular communications to upload physiologic data (CPAP adherence, applied CPAP pressure, mask leak, and residual respiratory events) to RedCap. Ecological momentary assessments (EMA) in the form of morning text message will allow patients and partners to report their sleep quality and CPAP experiences in the mornings over the first 6 weeks of enrollment.⁷⁵ Shortly after waking, patients and their bed partners will receive automated interactive text messages up to 4 times per week asking them about their sleep duration, quality, and experiences with CPAP from the prior night. Their responses will be uploaded directly into RedCap for comparison to nightly CPAP machine usage reports. Couples in the intervention arm will receive automated text messages when their CPAP usage drops below designated thresholds or when there is substantial improvement in CPAP adherence.⁵³ Mosio text messaging software will be used to automatically send and receive text messages between study participants and RedCap.

STUDY TASKS	USUAL CARE ARM	COUPLE-ORIENTED INTERVENTION ARM
Care from sleep providers	
 - Order CPAP - Counsel patient about OSA diagnosis 	
 - Order CPAP - Counsel patient about OSA diagnosis

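### The Aim 2 model names its random effects without a couple term and its covariates without the baseline score, and does not say whether patients and partners are modelled together or apart

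*Protocol*

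**What the plan says.** Section 2.0 of the protocol words the Aim 2 hypothesis for couples: "couples who receive the couple-oriented intervention will have a higher quality of sleep, functional status, and quality of life at 90 days". Section 4.0 lists the endpoints by both roles, for example "Patient and Bedpartner quality of sleep at 90 days". In section 6.0, "Patients will be randomized to a usual care arm or a couple-oriented intervention arm"; the partner follows the patient's allocation.

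Section 17.0 gives the analysis. For Aim 1, "Linear mixed effects models using random effects will be used to adjust for clustering of patients within sleep provider". The fixed effects listed there are body mass index, apnoea-hypopnoea index, gender and treatment. The treatment effect is tested by a Wald test with a robust standard error, whose clustering level is not given. Aim 2 is to be analysed in the same way, with the scales taken "for both patients and their bed partners". If the scores are not normally distributed, "we will use proportional odds with random effects by study site and sleep provider".

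No couple-level random effect, cluster or summary score appears in the protocol. Nor does a statement on whether the two roles share a model. Section 6.0 has all participants complete the instruments at baseline as well as at 30 and 90 days, but the baseline score is not among the listed covariates.

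**The concern.** The protocol names its random effects twice. Both times it leaves out the couple, which is the level at which its own hypothesis is worded and at which allocation acts. The two members of a couple share a bed, the disturbance from the sleep apnoea and the study arm. Section 2.0 itself says that untreated disease harms the partner's sleep and daytime functioning. Their scores are therefore likely to be positively correlated.

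If someone follows section 17.0 literally and stacks patients and partners in one data set, the model has nothing to absorb that correlation beyond what all couples of the same provider share. The confidence interval for the arm effect would be too narrow and the test too liberal.

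There are also signs that the Aim 1 model was carried over without being adapted. The apnoea-hypopnoea index comes from the patient's sleep study, and nothing provides one for the partner. The baseline score, which matters for a questionnaire outcome but has no counterpart for nightly device use, is missing. A study-site random effect is named although sections 12.0, 24.0 and 25.0 describe one health system only.

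**Working it through.** The protocol gives no power calculation, effect size, standard deviation or within-couple correlation, so there is no stated figure to reproduce. What can be checked is what happens if the listed model is fitted to both roles at once.

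**Inputs from the protocol**
- Sample size (section 1.0): "20 patients and 20 bed partners", so 40 people in 20 couples.
- Allocation (section 2.0): "Half of the patients will receive optimal" usual care, so about 10 couples per arm.
- Providers (section 25.0): 7.

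**Assumptions**
- Within-couple correlation ρ, given provider: 0.2 to 0.5.
- Equal variance σ² in the two roles.
- Two-sided 5% level, inferred from the planned 95% interval.

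**Standard error of the arm difference, both roles pooled**
- Without a couple term: variance = 2 × σ²/20 = 0.10σ², SE = 0.316σ.
- With the correlation: variance = 0.10σ² × (1 + ρ).
  - ρ = 0.2: 0.12σ², SE = 0.346σ.
  - ρ = 0.5: 0.15σ², SE = 0.387σ.
- Ratio of true to reported SE = √(1 + ρ): √1.2 = 1.10 and √1.5 = 1.22.

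**Actual error rate at nominal 5%:** 2 × [1 − Φ(1.96/√(1 + ρ))]

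| ρ (assumed) | SE ratio | Effective number of people, 40/(1 + ρ) | Error rate |
|---|---|---|---|
| 0.2 | 1.10 | 33.3 | 7.4% |
| 0.3 | 1.14 | 30.8 | 8.6% |
| 0.5 | 1.22 | 26.7 | 11.0% |

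**Check by simulation under no effect** (10 against 10 couples, 7 providers, 3,000 runs per setting)

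| Analysis | ρ = 0.1 | ρ = 0.3 | ρ = 0.5 |
|---|---|---|---|
| Pooled t-test on 40 people | 6.6% | 7.6% | 10.3% |
| Wald test, robust SE without clustering | 7.3% | 8.8% | 11.6% |

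Over correlations from 0 to 0.5, a t-test on couple means held 4.5% to 5.2%. Robust standard errors clustered by couple gave 6.0% to 7.0%; the remaining excess is a small-sample effect. Clustering by provider gave 11% to 12% at every correlation, including zero, because there are only about 7 clusters. The robust Wald test in section 17.0 therefore does not by itself settle the matter: the outcome depends on a clustering level that the protocol does not state.

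**Separate models.** With one record per couple in each model, the within-couple correlation does not enter, and none of the inflation above arises.

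**The case against.** The best defence is that the protocol never says the roles will be pooled. The Aim 1 model is written for one outcome per patient, and applying it to each role in turn is at least as natural a reading. Separate models are valid as they stand. That is right, so the inflation above describes one of two open readings and not a settled plan.

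A reader might infer that separate models would leave the Aim 2 hypothesis untested because it speaks of couples. The protocol does not support that. The aim itself refers to patients and their partners, the endpoints are listed by role, and no couple score or averaged effect is defined. Role-specific arm comparisons reasonably address what is written.

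A reader might also expect a joint model to bring fewer tests and more power. Neither follows. Role-specific effects must still be reported, so the number of comparisons does not fall. The role-averaged effect does have a smaller standard error than a single-role effect, by √((1 + ρ)/2) = 0.775 to 0.866 for ρ = 0.2 to 0.5, but it is a different quantity. If the partner effect were half the patient effect (an assumption for illustration), the average would be 0.75 of the patient effect. Its ratio to the standard error would be 0.75/0.775 = 0.97 to 0.75/0.866 = 0.87 of the patient-only ratio, which is a loss.

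Finally, joint or separate modelling could be left to a statistical analysis plan, and none is shown. But section 17.0 does not leave the structure open: it names the random effects and the covariates. What it names is unsuitable for pooled data and incomplete for the baseline score.

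**Conclusion.** The point holds in a limited form. Section 17.0 specifies the Aim 2 random effects without a couple term, omits the baseline score from the listed covariates, and does not say whether the roles are modelled together or apart. If they are modelled together as written, the standard error is understated by a factor of 1.10 to 1.22 and the error rate is about 7% to 11% instead of 5%. These figures rest on an assumed within-couple correlation of 0.2 to 0.5, for which the protocol gives no value, and on equal variances in the two roles. If the roles are modelled apart, there is no error inflation and only the baseline adjustment and the site term need attention.

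The primary adherence outcome is measured on patients only and is not affected. Aim 2 concerns secondary outcomes in a pilot of 20 couples, so the severity is modest. The change is still worth making because it is cheap and removes an avoidable ambiguity.

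**What to change.** State one of two options in section 17.0.

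1. **Joint model.** First say which instruments are valid for both roles; this needs a decision for the sleep-apnoea-specific quality-of-life index. For each such instrument, fit one model with fixed effects for arm, role and arm-by-role, the person's own baseline score on that instrument, and a random intercept for couple. Carry the couple intercept into the proportional-odds fallback too. Report the arm effect for patients and for partners alongside the role-averaged effect.
2. **Separate models.** State that patients and partners are analysed in separate models, each adjusted for the baseline score of the same instrument. No couple term is then needed.

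Under either option, remove the study-site random effect, which cannot be estimated when one health system is the only site.

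The cost is a short paragraph and slightly more analysis work; the baseline scores are already being collected. The small downside of the joint model is that the averaged effect can hide different effects in the two roles, which is why the role-specific effects must be shown with it. It should not be presented as reducing the number of tests or as a general gain in power.
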